#### 3.3 Primary outcome

Time to successful weaning: duration from the baseline ABG confirming selection criteria are met, to final removal of the ventilator. Weaning will be considered successful when there has been no recurrence of AHRF requiring replacement of NIV within 48 hours of discontinuation of NIV. Recurrent AHRF more than 48 hours after removal of the ventilator will be considered relapse. Death precludes weaning and will be captured in a competing risk analysis.

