#### 3.4 Secondary outcomes

- 1. Relapse requiring NIV (defined as recurrent AHRF>48 hours after removal of ventilator).
- 2. Total duration of ventilation.
- 3. Length of hospital stay.
- 4. NIV complications (incidence and severity).
- 5. Patient reported outcome measures: Modified Borg dyspnoea scale\*; Sputum clearance via visual analogue scale\*; Richards-Campbell sleep questionnaire\*; Hospital Anxiety and Depression Scale (HADS) pre-discharge; St Georges Respiratory Questionnaire for COPD (SGRQ-C) and EQ-5D-5L days 7, 30 and 90 post-randomisations.
- 6. Mortality in-hospital and 90-days post-randomisation.
- 7. Readmissions 30-days post-discharge.
- 8. Health economic analysis:
  - Costs to the NHS in terms of provision of the interventions (both on a respiratory support unit and a critical care unit) and cost implications of subsequent resource utilisation up to 90 days follow up;
  - Cost utility analysis using EQ-5D-5L quality adjusted life years (QALYs).
- 9. Responder analysis within the accelerated weaning group to identify predictors of success/failure.
- \*Day 1 to 5.

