#### 6.1 Inclusion criteria

- 1. Clinical diagnosis of Exacerbation of Chronic Obstructive Pulmonary Disease\*, complicated by acute hypercapnic respiratory failure (pH<7.35 and PaCO2>6.5kPa).
- 2. Age 35 years or over.
- 3. Smoking history of 10+ pack years.
- 4. Low or medium risk Non-Invasive Ventilation (NIV) Outcomes score.
- 5. Provision of acute NIV for 24 hours or longer.
- 6. Correction of respiratory acidaemia.
- 7. Able to tolerate 60 minutes of unsupported breathing, confirmed by arterial blood gas† (ABG). This is the qualifying ABG.
- 8. PaCO2 <8kPa, or PaCO2 8-9kPa with at least a 20% fall in PaCO2 from pre-NIV baseline value, with pH  $\geq$ 7.35 on the qualifying blood gas.
- 9. Participants must be randomised within 24 hours of meeting the weaning criteria (based on the time of the qualifying ABG).
- \*Confirmation of airflow obstruction is not required (often unavailable on admission). Patients should have 1-year plus history of breathlessness, with or without cough and sputum production, consistent with a diagnosis of COPD.

<sup>†Capillary blood gas will be accepted.

ISRCTN: 64639614 IRAS: 313485 CPMS: 53277

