#### 7.6 Baseline Data

A separate source document worksheet (collecting the following data) and manual will be provided to all participating sites. The case report form is electronic (REDCap). Key data are shown in Table 1.

Table 1. Key data for source document worksheet.

Category	Data
Patient demographics	Name; NHS number. Hospital number; Gender; Age; Ethnicity; Multiple index of deprivation decile; Recruiting Site, Participant identifier generated at randomisation.
COPD diagnosis	Previous spirometry; Discharge spirometry (if required); Exacerbation history; NIV history; LTOT prescription; Covid-19 history; Previous lung surgery.
Admission indices	Date and time of arrival at hospital; Date and time clinician contacted to start NIV; Date and time NIV mask applied; Where NIV started and continued; Date and time patient moved to dedicated NIV area; Observations on arrival; Chest x-ray changes; ECG; Date and time of discharge from hospital; Mortality.
Risk stratification	NIV Outcomes score; eMRCD; DECAF; Apache II score; Charlson index.
Blood results	Full blood count indices.
Past Medical History	Various cardiovascular, respiratory and immunodeficiency variables.
Medication history	Bronchodilators, cardiovascular and antibiotic medications.
Social history	Home circumstances; smoking history; employment; Rockwood clinical frailty score; baseline function.
Blood gases	pH; PaCO 2 ; PaO 2 ; HCO 3 -; BE; SaO 2 .
NIV data	IPAP; EPAP/PEEP/CPAP; PS; Back up rate; Respiratory rate; Tidal volumes; Minute ventilation; Patient trigger, Interface used, Weaning plan; Complications; Date and time NIV removed; Relapse.

ISRCTN: 64639614 IRAS: 313485 CPMS: 53277

Observations	SpO2; Blood pressure; Heart rate; Temperature.
Randomisation	Standard weaning protocol; accelerated weaning protocol.
allocation	
Patient	Borg breathless scale; Phlegm visual analogue scale; Richards-
reported	Campbell sleep questionnaire; Hospital Anxiety and Depression scale; St
outcome	Georges Respiratory Questionnaire (COPD); EQ-5D-5L.
measures	
Trial outcomes	Readmissions; Mortality; Health economics (GP attendances;
	Emergency Department attendances; Readmission to hospital).

Respiratory Rate: **count** the number of breaths observed in 1 minute.

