#### 10.3.3 Secondary outcome analysis

For all outcomes (both primary and secondary) we will present the characteristics, including those stratified by the weaning strategies. We will describe all baseline characteristics, follow-up measurements using suitable measures of tendencies: means and median with the associated standard deviation, 95% confidence interval and interquartile ranges for continuous variables and frequency and proportions for categorical variables (including binary variables). We will use Chi-Square test (or Fisher's Exact test in case of small number of observations) if the variable is categorical and will use t-test if the variable is continuous. For variables that are not parametric we will use Mann-Whitney U test. We will use the critical alpha 5% (thus p-value < 0.05 will be considered statistically significant) and we will also present the 95% confidence interval. Analyses will be performed by intention to treat, with secondary analyses of primary and secondary outcome based on protocol adherence. All analyses will be done in  $R^{15}$  and SPSS.  $R^{16}$ 

All baseline patient characteristics and outcomes will be included in the imputation mode. Mean change in quality of life over 90 days (SGRQ-C, EQ5D5L) from baseline will be calculated. In-hospital and 90-day mortality, and readmission within 30-days: time from discharge to death and time to readmission will be analysed using a Cox proportional hazards regression model, adjusted for covariates. For this analysis, no interaction between interventions will be assumed. Analysis will be two-sided at 5% level. We will also report the model performance by C-statistic. A sensitivity analysis will be performed with the log-rank test stratified by the centre. As we are only capturing readmission within 30 days, we will compare the proportion adjusted for the covariates (In-hospital mortality=NIVO; Readmission=PEARL: previous admission, extended MRC Dyspnoea scale, age, left and right heart failure).

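### Total ventilation time, and to a lesser extent hospital stay, appear to include uncapped time before allocation yet are compared without adjustment, which costs precision but does not bias the result

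*Protocol*

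**What the plan says.** Protocol section 3.4 names outcome 2 as "Total duration of ventilation" and outcome 3 as "Length of hospital stay". Neither has a stated time origin. In the same list, the quality-of-life questionnaires and 90-day mortality are tied to randomisation, and readmission is tied to discharge.

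The primary outcome in section 3.3 does have an origin: "Time to successful weaning: duration from the baseline ABG confirming selection criteria are met, to final removal of the ventilator".

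Section 6.1 makes "Provision of acute NIV for 24 hours or longer" an inclusion criterion, with no upper limit. It also states: "Participants must be randomised within 24 hours of meeting the weaning criteria". That limit covers only the gap between the qualifying blood gas and randomisation, not the NIV given before the blood gas.

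For continuous secondary outcomes, section 10.3.3 "will use t-test if the variable is continuous", and adds: "For variables that are not parametric we will use Mann-Whitney U test". It names covariate adjustment only for mortality and readmission. Hours of earlier NIV are not a minimisation factor in section 7.3.

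**The concern.** The primary clock already starts at the qualifying blood gas. A separate outcome called a total duration therefore has a distinct meaning mainly if it reaches back to the start of NIV. Table 1 in section 7.6 fits that reading: it collects "Date and time NIV mask applied" together with arrival, NIV removal and discharge times.

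On that reading, each total is the sum of a part completed before allocation and a part that allocation can change. The first part cannot differ between arms except by chance, but it does vary from patient to patient. A two-group test on the sum carries that variation as noise. The trial is sized only for the primary outcome, so precision on the secondary outcomes is not protected, and here some can be recovered at almost no cost. At stake is how clearly the trial can describe the effect on overall NIV exposure and hospital stay.

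**Working it through.** **1. The plan's own figure.** The only sample size stated is for the primary outcome (section 10.1). Inputs: weaning incidence 0.50 against 0.667 and death 0.054 in both arms at 2.71 days, two-sided 5%, power 80%, 10% attrition. I assume constant cause-specific hazards.

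- Standard arm, hazard × time: −ln(1 − 0.554) × 0.50/0.554 = 0.729
- Accelerated arm: −ln(1 − 0.721) × 0.667/0.721 = 1.181
- Ratio: 1.181/0.729 = 1.62
- Events: 4 × (1.960 + 0.842)² / (ln 1.62)² ≈ 135 (stated 69 + 67 = 136)
- Eventual weaning probability: 0.903 and 0.925, mean 0.914, so 135/0.914 ≈ 148 evaluable, or 74 per arm
- With attrition: 148/0.9 = 164.4 (stated 164)

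The stated size reproduces. It concerns an outcome that this point does not touch. I carry forward 74 evaluable per arm.

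**2. Variance of a whole-episode total.** If the two parts are independent, SD_total = √(SD_post² + SD_pre²), where post means after the qualifying blood gas. The fixed 24-hour minimum adds nothing to SD_pre; only the variable excess does. The difference between arms is unchanged.

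**3. Power for ventilation time.** Power ≈ Φ(24 / (SD_total × √(2/74)) − 1.96). The 24-hour difference is borrowed from the section 10.1 assumption on weaning time. All SDs are assumptions.

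| SD_post | SD_pre 0 h | 12 h | 24 h | 36 h | 48 h |
|---|---|---|---|---|---|
| 40 h | 95% | 94% | 88% | 77% | 65% |
| 50 h | 83% | 81% | 75% | 66% | 56% |
| 80 h | 45% | 44% | 42% | 38% | 35% |

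Worked cell (50 h, 24 h): SD_total = √(2500 + 576) = 55.5; 24/(55.5 × 0.1644) = 2.63; Φ(2.63 − 1.96) ≈ 75%.

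From the unrounded values, the losses against SD_pre = 0 are about 1 to 2 points at 12 h, 3 to 8 at 24 h and 10 to 31 at 48 h.

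**4. Power for length of stay.** Same formula, with an assumed 1-day difference.

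| SD_post | SD_pre 0 d | 1 d | 2 d |
|---|---|---|---|
| 3 d | 53% | 49% | 39% |
| 5 d | 23% | 22% | 20% |
| 7 d | 14% | 14% | 13% |

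At SD_pre = 1 day the loss is 0 to 4 points. It becomes material only if stay before the blood gas varies widely and stay after it varies little.

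**5. Does adjustment recover the loss?** Simulation, 1,000 replicates per setting, 74 per arm, exponential times after the blood gas with medians 65 and 41 h (41 = 65 − 24), and SD_pre = 24 h. Power at two-sided 5%:

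| Correlation of the two parts | t-test from qualifying blood gas | t-test on total | Total, adjusted for prior hours |
|---|---|---|---|
| 0 | 79% | 75% | 79% |
| 0.3 | 78% | 67% | 80% |

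Adjustment restores the power. If slow early recovery also predicts slow weaning, the unadjusted loss is larger than independence suggests. The 65 and 41 hours are elapsed weaning times, which include breaks off NIV. They stand in for ventilated hours here because the protocol gives no other figure.

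**The case against.** The whole-episode reading is an inference, since neither outcome has a stated origin, and details of unpowered secondary outcomes are often left to an SAP. This stands in part. However, the protocol itself fixes the unadjusted tests, and the word total points beyond the primary clock.

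Whole-episode burden is also a legitimate quantity. Section 2 speaks of savings from a shorter overall stay, and the primary outcome already isolates the weaning period. This stands: nothing requires the totals to be dropped. A reader might infer that both outcomes must restart at randomisation. That would change the estimand, overlap heavily with the primary outcome and add a further clock.

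The size rests entirely on assumed spreads, and the upper end is doubtful. Taking 24 hours, plus an exponential excess with mean (and SD) 12, 24 or 48 h, plus a post-blood-gas median of 65 h, implies control medians for the total of about 102, 114 and 135 to 140 h. Section 2 gives centre-level durations of 31.5 to 95.5 h. That cohort is broader and its durations may be counted differently, so this is only indicative, but it argues against relying on the 48-hour column.

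A reader might also infer bias, because a chance imbalance in earlier NIV time would show up in both totals. The documents do not support that: allocation is randomised, and ordinary standard errors already cover chance imbalance. Minimisation on site, NIVO risk, pH, bicarbonate and previous NIV may balance some of it as well.

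**Conclusion.** The point holds as one of precision on two secondary outcomes. On the natural reading, both totals include variable time that neither strategy can change, and the named tests leave it in the error term. For ventilation time the loss runs from negligible (1 to 2 points at a pre-allocation SD of 12 hours) through 3 to 8 points at 24 hours to 10 to 31 points at 48 hours. For length of stay it is 0 to 4 points at an SD of 1 day. These figures assume a 24-hour and a 1-day difference, 74 per arm, independence of the two parts and SDs that the protocol does not give.

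One might go further and say that the main claim of less NIV is weakened. It is not: that claim rests on the primary outcome, which starts at the qualifying blood gas, and the sample size of 164 is unaffected.

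**What to change.** State the time origin of both outcomes. Keep the whole-episode totals, but compare them by regression on treatment arm, adjusted for the duration before the qualifying blood gas: from NIV mask application for ventilation time, and from hospital arrival for length of stay. Both covariates are complete before randomisation, so adjusting for them is safe. If the totals are skewed, robust or bootstrap standard errors can be used.

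Alternatively, count both outcomes from the qualifying blood gas, as the primary outcome does. The t-test or Mann-Whitney test can then stay, and the whole-episode totals are reported descriptively. Under either option, up to 24 hours between the blood gas and randomisation remains in the outcome, as it does in the primary.

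The cost is a few sentences in sections 3.4 and 10.3.3. Arrival, mask application, NIV removal and discharge times are already in Table 1, and the time of the qualifying blood gas is needed for the primary outcome. No new data, visits or participants are required.

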### 4. Trial Design

A multi-centre, open-label, parallel, randomised controlled trial.

Our position is one of equipoise. The randomised controlled trial design will provide a definitive result as to the better outcome for patients: a) a standard wean may provide a longer duration of NIV wean, with lower PaCO2 at discharge, with less relapse and readmissions; or b) an accelerated wean may mean a shorter duration of NIV wean, but with more relapse requiring NIV, and more readmissions.

IRAS: 313485 CPMS: 53277

#### 5. Trial Setting

Patients will be recruited from at least seven secondary care centres across the UK, with different structures of care, to ensure that the results are applicable across the NHS. The centres have been carefully selected, based on current standard weaning time from acute NIV, and with PIs for each site confirming their commitment to adhere to the weaning protocols.

Confirmed recruiting sites are: 1) Northumbria Healthcare NHS Foundation Trust; 2) Newcastle Upon Tyne NHS Foundation Trust; 3) North Tees and Hartlepool NHS Foundation Trust; 4) The Leeds Teaching Hospitals NHS Trust; 5) Royal United Hospitals Bath NHS Foundation Trust; 6) University Hospitals Plymouth NHS Trust; 7) Nottingham University Hospitals NHS Trust; and 8) University Hospitals of Leicester NHS Trust.

Patients requiring NIV are managed on critical care or respiratory support units, and will be identified by daily screening by the usual care team.

#### 6. Participant Eligibility Criteria

The selection criteria identify patients who have received more than 24 hours NIV and have improved sufficiently to consider weaning.

#### 6.1 Inclusion criteria

- 1. Clinical diagnosis of Exacerbation of Chronic Obstructive Pulmonary Disease\*, complicated by acute hypercapnic respiratory failure (pH<7.35 and PaCO2>6.5kPa).
- 2. Age 35 years or over.
- 3. Smoking history of 10+ pack years.
- 4. Low or medium risk Non-Invasive Ventilation (NIV) Outcomes score.
- 5. Provision of acute NIV for 24 hours or longer.
- 6. Correction of respiratory acidaemia.
- 7. Able to tolerate 60 minutes of unsupported breathing, confirmed by arterial blood gas† (ABG). This is the qualifying ABG.
- 8. PaCO2 <8kPa, or PaCO2 8-9kPa with at least a 20% fall in PaCO2 from pre-NIV baseline value, with pH  $\geq$ 7.35 on the qualifying blood gas.
- 9. Participants must be randomised within 24 hours of meeting the weaning criteria (based on the time of the qualifying ABG).
- \*Confirmation of airflow obstruction is not required (often unavailable on admission). Patients should have 1-year plus history of breathlessness, with or without cough and sputum production, consistent with a diagnosis of COPD.

<sup>†Capillary blood gas will be accepted.

ISRCTN: 64639614 IRAS: 313485 CPMS: 53277

#### 6.2 Exclusion criteria

- 1. Poor tolerance of NIV likely to limit adherence to protocol.
- 2. Receiving home ventilation on admission, or planned referral for home ventilation on discharge.
- 3. Inability to provide informed consent.
- 4. Failure of another organ requiring level 2 or 3 organ support.
- 5. Clinically significant pulmonary fibrosis.
- 6. Metastatic Cancer, advanced haematological malignancy, or other serious comorbidities, which may influence survival or decisions about ventilation within the time-frame of the trial (3 months).

We will exclude few patients, and only on objective criteria compromising the validity of the research.

We will assist recruitment and retention of any patients with language or communication barriers. A video covering the full patient information sheet details will aid recruitment and the consent process.

#### 7. Trial Procedures

A schedule of activities is included in this application (appendix 1). All inpatient assessments will be completed on the scheduled day. Assessments within 30 days post-discharge from hospital will be completed within 10 days of the scheduled visit, in the patient's home, outpatient setting, or via telephone. Assessments within 90 days post-randomisation will be completed within 14 days of the scheduled visit, in the patient's home, outpatient setting, or via telephone.

## 7.1 Recruitment

Patients who will potentially be eligible for the trial (ECOPD with AHRF requiring NIV who have low or medium risk NIVO score), will be provided with a summary patient information sheet (PIS) at initiation of NIV. This basic information about the trial will be available (one side of A4, large font) to support initial discussions between the usual care team and potentially eligible patients. However, patients will not be asked for consent or randomised at the time of acute presentation and initiation of NIV.

At all participating sites, patients who require acute NIV are managed on dedicated units (critical care or respiratory support units).

Recruitment and any facilitators or barriers identified across all sites will be discussed at the monthly trial management group meetings to share best practice. Feedback from trial participants will also be captured, reviewed by our PPI group, and shared with the trial management group and steering committee.

Will we be recording the details of patients who are not eligible for the trial in a screening log: patients with ECOPD requiring acute NIV, who have low or medium risk NIVO score, but are not recruited.

#### 7.1.1 Participant Identification

Patients admitted to critical care and respiratory support units will be identified using the eligibility criteria and approached to discuss the trial by the usual care team at all sites.

ISRCTN: 64639614 IRAS: 313485 CPMS: 53277

Eligibility will be confirmed by the research team, on a source document worksheet, from historic and current, electronic and paper based clinical information.

#### 7.1.2 Screening

Patients will be identified by daily screening on critical care and respiratory support units. We will be seeking consent when patients will still be receiving ventilation for an exacerbation of COPD, and may have only short breaks off the ventilator. The timing of randomisation and allocation to the weaning protocols under investigation is time critical. Patients must be randomised within 24 hours of meeting eligibility criteria. To meet eligibility criteria, patients will be required to have an arterial blood gas taken off NIV (part of usual care), and the blood gas result to be satisfactory to meet eligibility criteria. We will provide education and training to the usual care NIV teams at all centres, and encourage early discussions about the trial with those who are potentially eligible. Once patients meet the physiological and clinical criteria that define the start of the weaning process, and eligibility for randomisation, we will provide full trial information.

#### 7.2 Consent

We have conducted two face to face group meetings with the Northumbria Lung Research PPI group. At the meetings, the consent process, and the content and terminology used in the Patient Information Sheet (PIS) was discussed. As a result, depending on patient preference, the patient can choose:

- a) to read the full PIS themselves;
- b) listen to the PIS being read to them; or
- c) watch a video recording of the full PIS being read.

Only members of the usual care team will approach patients in the first instance to provide the patient information and answer any initial questions from the potential participants. With the patient's agreement, the research team will be available to discuss the trial and answer any additional questions or concerns arising. Written consent will be taken by members of the research team. Interpreters will also be available when possible if required. Consent will only be taken by individuals who have the appropriate GCP training, before any trial procedures or assessments are undertaken. There is a named Principle Investigator for each site who retains overall responsibility for the conduct of research at their site, including taking informed consent from participants.

Informed consent will be taken and then randomisation performed, only once patients have improved sufficiently to meet criteria for weaning from NIV (defined in the inclusion criteria). Only a minority of patients experience carbon dioxide narcosis or delirium with hypercapnic respiratory failure; such patients would only be given information once this had resolved.

We have allocated an average of 60 minutes for the consent process, in recognition that patients will still be receiving acute NIV. All participants will be aged 35 years or older.

